In objective 2, we will examine whether the everolimus group will show more improvement, compared to the placebo group, on the main neurocognitive efficacy composite outcome. Randomization Group (everolimus versus placebo) differences on the neurocognitive composite will be analyzed using mixed effects (growth curve) modeling, fully utilizing repeated measurements collected at three points (Time: baseline, 3-month follow-up, and 6-month follow-up). A significant interaction between Time and Randomization Group, with the everolimus group showing a more favorable outcome trajectory, will support the primary efficacy hypothesis. Maximum likelihood estimation will be implemented in the Mplus program version 7.2 or above.

Mixed effects (growth curve) model analyses will be conducted following the intention-to-treat principle. Data points that are missing due to subject attrition will be handled assuming that data are missing at random (MAR) conditional on observed information, which is less restrictive than missing completely at random (MCAR) assumed in fixed effects analyses such as ANCOVA and regression analysis. In this procedure, all available cases including the ones with missing information will be included in the analyses. By including every subject who completed at least one assessment, we are not only more likely to conserve power, but also less likely to produce biased effect estimates. In mixed effects analyses, the slope of the outcome will be modeled as the key

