dependent variable predicted by randomization group. We will conduct the analysis with and without conditioning on relevant baseline covariates. The results of these longitudinal analyses can be easily converted to a cross-sectional group effect at each assessment time point to describe the magnitude and significance of group differences. Of particular interest is the group difference at end of treatment (6-month assessment). The mixed effects analyses will be repeated using a model where the baseline scores on each outcome are treated as a baseline covariate to control for (instead of as a part of) the repeated measures. This model can be useful if there is a considerable heterogeneity between before and after treatment processes. We will also analyze the data using conventional ANCOVA treating the end point neurocognitive composite as the dependent variable and controlling for the baseline neurocognitive composite. Further analyses will be conducted using the same analysis models but with transformed data (e.g., log transformation) to check the sensitivity of the results to deviation from outcome normality. Statistical significance of all main effects and interaction terms as well as cross-sectional group differences will be determined using a one-tailed Type 1 error rate of α =.05. The same analysis strategy will be employed for secondary efficacy outcomes and a false discovery rate correction will be implemented to control inflation of Type 1 error.

If the exploratory biosample objectives are pursued, we will explore whether baseline peripheral blood levels of PTEN-associated pathway molecules (PI3K/AKT, mTOR, MAPK protein levels) change with treatment and if changes in peripheral pathway molecules correlate with clinical improvement. To determine whether PTEN-associated pathway molecules change with treatment, we will use a similar mixed effect (growth curve) modeling approach to that described above for Secondary Objective with screening, 3-month, and 6-month pathway measurements as outcome measures. The Time by Randomization Group interaction will test whether the everolimus treatment group shows improvement/normalization of PTEN-pathway molecule levels relative to placebo. This component will be dependent on securing additional funds.

In analyzing the resting state EEG and AEP data we will focus on the following:

- 1. Baseline EEG gamma power
- 2. AEP N1 habituation

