Secondary Objective – Efficacy. For power estimation purposes, the variability in PTEN patients treated with an mTOR inhibitor is expected to be similar to the untreated sample. Preliminary data indicates that the measures which comprise the dominant portion of the neurocognitive composite index (processing speed working memory, and fine motor) are highly sensitive to the brain dysfunction seen in PTEN patients with ASD. The effect sizes are approximately 1 SD or larger. In a comparison between mTOR treated vs. untreated PTEN patients, an effect size of at least 0.65 SD would be of interest and represent clinically- meaningful improvement. For example, an effect size of at least 0.65 SD on cognitive measures would translate to a 10-point standard score improvement in the everolimus-treated group relative to placebo. An improvement of 10 or more points is outside the standard error of measurement for most cognitive measures and is typically considered a reliable change when disordered populations are re-tested.

A sample size of 40 (20 per arm) patients will permit detection of endpoint (6-month follow-up) differences of at least 0.80 SD at the 5% significance level (one-sided alpha = 0.05) with 80% power (1- β). Statistical power will be weaker (1- β =.65) if smaller cross-sectional differences are observed (0.65 SD). However, statistical power is very strong, even for smaller differences (Cohen's d≥.50 equivalent to ≥.50 SD difference) when the full repeated measures nature of the design is considered – baseline, 3-month follow-up, 6-month follow-up. Assuming even modest correlations between repeated measurements of outcome variables (r≥.30), power to detect clinically meaningful differences of .50 SD is very good (1- β =.83; one-sided α =.05). If the primary outcome measure (neurocognitive composite) meets nominal statistical significance in the expected direction (one-tailed p<.05) or a secondary outcome measure meets a more stringent false discovery rate-corrected

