significance level in the expected direction, these outcomes will be considered candidates for Phase III confirmatory trial evaluation. To determine if a secondary outcome meets the more stringent false discovery rate-corrected significance level, a Benjamini-Hochberg false discovery rate correction will be applied with adjustment for all secondary outcome measures. This adjustment involves sorting the list of obtained p-values in descending order. The smallest p-value is then compared to the most stringent alpha, the next smallest is compared to the next most stringent alpha, and so on. Only those secondary outcomes meeting FDR-corrected alpha level will be considered candidates for Phase III evaluation.

An interim analysis will be conducted after half the sample has been collected (10 patients in each arm) and will mainly focus on safety. Efficacy interim analysis may be under-powered, but will focus on whether the effects are in the expected direction and whether effect sizes (both the endpoint effect size and the interaction fully utilizing repeated measures) are approaching expected levels (at least Cohen's d≥.30). The goal of the interim analysis for efficacy will be to get a signal that will allow us to design more targeted trials in the future. As such, we will check for a signal in any domain and, if needed, include additional endpoints before the end of the study to expand the endpoint and optimize outcome.

Additional considerations. This is the first clinical trial in patients with PTEN mutations and ASD/DD. For this reason, and to facilitate recruitment, all types of PTEN mutations will be permitted within the randomized patients. However, post-hoc analyses will be completed to examine the existence of any differential effect of treatment based on the type of PTEN mutation (missense vs. other mutation types) or mutation location (exon number, location in 3-D PTEN structure).

18. Protocol Amendments or Changes in Study Conduct

Any change or addition (excluding administrative) to this protocol requires a written protocol amendment that must be reviewed by the central IRB at Boston Children's Hospital (Boston and Stanford only), Cleveland Clinic IRB the NIH, and Novartis as applicable. Amendments significantly affecting the safety of subjects, the scope of the investigation or the scientific quality of the study require additional approval by the IRB at each study center. A copy of the written approval of the IRB must be provided to Novartis.

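### With about 40 patients, the main efficacy test is fitted by maximum likelihood with no small-sample correction named; its one-sided error is about 5–6.7% if read as a Wald z test, depending on the covariance model

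*Combined protocol and SAP*

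**What the plan says.** Section 17 (objective 2) analyses the neurocognitive composite with a mixed-effects growth curve model, "fully utilizing repeated measurements collected at three points (Time: baseline, 3-month follow-up, and 6-month follow-up"). The deciding test is the interaction: "A significant interaction between Time and Randomization Group, with the everolimus group showing a more favorable outcome trajectory, will support the primary efficacy hypothesis". On estimation it says only that "Maximum likelihood estimation will be implemented in the Mplus program version 7.2 or above". Significance of all terms "will be determined using a one-tailed Type 1 error rate of α =.05".

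The same strategy applies to the secondary efficacy outcomes, with a false discovery rate correction. Section 17.1 identifies this as Benjamini-Hochberg over all secondary measures. It makes a one-tailed p below 0.05 on the composite a route to Phase III candidacy, and for the secondary outcomes states: "Only those secondary outcomes meeting FDR-corrected alpha level will be considered candidates for Phase III evaluation".

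Section 17 gives no covariance structure for the repeated measures and no reference distribution. It does not mention REML, Kenward-Roger or Satterthwaite degrees of freedom, a bootstrap or a permutation test. It also plans versions with baseline covariates (number not given) and, as a further analysis, a conventional ANCOVA at the 6-month endpoint.

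**The concern.** Maximum likelihood divides residual sums of squares by the number of patients rather than by the residual degrees of freedom, so its standard errors are a little too small. A Wald ratio read against the normal distribution also ignores the uncertainty in the variance estimate, so the critical value is a little too low. Both errors favour rejection. They are negligible in large trials but visible at 20 per arm.

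The relative error grows in the tail. A Benjamini-Hochberg procedure over about 20 outcomes starts near 0.05/20 = 0.0025, where a shortfall of a few percent in the standard error matters more than it does at 0.05. At stake is how often an outcome is put forward as a Phase III candidate by chance.

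**Working it through.** **Inputs from the plan.** 40 patients, 20 per arm; three visits; one-sided α = 0.05; maximum likelihood; about 10% dropout (section 17.1).

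**Assumptions.** The test is a Wald z test. There are 12 to 23 secondary outcomes; the plan gives no count, and about 23 can be counted in Table 12. There are 0 to 4 covariates.

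**The plan's own power figures.** Section 17.1 says: "A sample size of 40 (20 per arm) patients will permit detection of endpoint (6-month follow-up) differences of at least 0.80 SD" with 80% power, and "Statistical power will be weaker (1- β =.65) if smaller cross-sectional differences are observed (0.65 SD"). The noncentrality is d × √(20/2).

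- d = 0.80: 2.530. Power is 0.812 by the normal distribution and 0.799 by t with 38 df.
- d = 0.65: 2.055. Power is 0.659 by the normal and 0.646 by t.

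Both stated values are reproduced, slightly better by the t calculation. The repeated-measures figure, "power to detect clinically meaningful differences of .50 SD is very good (1- β =.83; one-sided α =.05"), reproduces as 0.827 from a within-between F test with f = 0.25, r = 0.30, noncentrality 0.25² × 40 × 3/(1 − 0.30) = 10.71, and 2 and 76 df. So the power figures fit finite-df tests, while the analysis text names none.

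**Homogeneous random-slope model, complete data.** Here z = t₃₈ × √(40/38), so the true error is P(t₃₈ > z₁₋α × √(38/40)).

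- α = 0.05: P(t₃₈ > 1.603) = 0.0586.
- α = 0.0025: P(t₃₈ > 2.736) = 0.0047, or 1.88 times nominal.

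If the slope variance is kept non-negative, simulation gives 5.0–5.6% at nominal 5%. One set of 1,969 random-slope fits with a small slope variance gave 4.9%. At 0.05/23 the range for this model is 1.2–1.9 times nominal.

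**Free visit-specific variances (unstructured covariance), linear means, complete data.** One further degree of freedom is lost, so the error is P(t₃₇ > z₁₋α × √(37/40)) when standard errors come from the observed information.

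- α = 0.05: P(t₃₇ > 1.582) = 0.0611.
- α = 0.0025: P(t₃₇ > 2.700) = 0.0052, or 2.08 times nominal.
- α = 0.05/23: 0.00467, or 2.15 times nominal.

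Simulation with expected-information standard errors gives 6.2–6.4% at nominal 5% and 2.3–2.4 times nominal at 0.05/23.

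**Dropout and covariates (unstructured model).**

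| Setting, 40 patients | Error at nominal 5% | Ratio at 0.05/23 |
|---|---|---|
| Complete data | 6.1–6.4% | 2.15–2.4 |
| 10% dropout (simulated) | 6.4–6.5% | 2.8 |
| 20% dropout (simulated) | 6.7% | 2.8 |
| 2 covariates, complete: P(t₃₅ > 1.645 × √(35/40)) | 6.6% | 2.6 |
| 4 covariates, complete: P(t₃₃ > 1.645 × √(33/40)) | 7.2% | 3.3 |

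Each dropout row rests on 40,000 null data sets per true covariance, with half of the dropouts lost after baseline and half after month 3.

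**Down the Benjamini-Hochberg ladder** (23 outcomes, unstructured, complete data, no covariates): 2.15 at rank 1, 1.85 at rank 2, 1.54 at rank 5, 1.38 at rank 10 and 1.22 at rank 23.

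**The case against.** The strongest reply is that the plan never says a z test will be used or that visit variances will be free. Section 17 describes the slope as the quantity predicted by group, which fits a homogeneous random-slope model; for that model the error is 5.0–5.9%. This stands as a limit on the size. It does not remove the point, because a growth curve with visit-specific residual variances fits the text equally well and nothing in section 17 chooses between them.

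Second, a reader might infer that the error is 6–7% in general and more than doubles at the false discovery rate thresholds as a whole. The documents do not support that. At the plan's 10% dropout without covariates the unstructured model gives 6.4–6.5%. Doubling is confined to the strictest steps under the less favourable covariance model. Nor can the sample be taken as 36: section 17 keeps every patient with at least one assessment, so dropouts remain in the model. The false discovery rate itself has not been computed.

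Third, the study is exploratory and mainly descriptive, efficacy is its secondary objective, and qualifying outcomes become candidates rather than being committed to Phase III. The planned ANCOVA, with its usual t test, is unaffected and would sit beside the mixed model. All of this lowers the consequence. But the ANCOVA is an additional analysis; the interaction is what the plan says will support the hypothesis, and section 17.1 attaches the candidate rule to p-values.

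**Conclusion.** The point holds at modest size. With 40 patients, maximum likelihood and a Wald z reference, the one-sided error at nominal 5% is about 5–6% under a homogeneous random-slope model and about 6–6.7% with free visit-specific variances. About 7% needs several covariates as well. At the strictest Benjamini-Hochberg step the error is roughly 1.2–1.9 times nominal for the simpler model and about 2–2.8 times for the unstructured one without covariates. It falls to about 1.2 times at the last step.

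This rests on three assumptions that the documents neither state nor exclude: a z reference, the covariance structure, and about 20 secondary outcomes. It is a desirable improvement to the plan, not a flaw that invalidates the trial.

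**What to change.** In section 17, objective 2, specify that the composite and all secondary-outcome models are fitted by REML with a named covariance structure and Kenward-Roger degrees of freedom. Base the p < 0.05 rule and the false discovery rate decisions on those p-values, and keep the Mplus maximum likelihood fit as a sensitivity analysis.

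The cost is other software for all of these models, not just one, and slightly larger p-values. For complete data the standard error rises by √(40/38) = 1.026 to √(40/37) = 1.040. With 38 df the critical value moves from 1.645 to 1.686 at 0.05, and from 2.852 to 3.033 at 0.05/23. On the plan's endpoint comparison at 0.80 SD, power goes from 0.812 to 0.799, about one point, and still rounds to the stated 80%. No extra patients or data are needed.

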Social Responsiveness Scale, Second Edition (SRS-2): Total T-score

Repetitive Behavior Scale - Revised (RBS-R): Total raw score

Improving Associated Behaviors

Behavior Rating Inventory of Executive Function (BRIEF): General executive composite and sub-scale scores Adult/Child Behavior Checklist (CBCL ARF/CBCL): Total problems T score Short Sensory Profile (SSP): Total Score

Improving Adaptive Behaviors

Vineland Adaptive Behavior Scales-III (VABS-III) Caregiver report: Composite and scale scores.

A measure of functional adaptive behavior, i.e. ability to cope with personal and social skills in everyday life that may be deficient in autism or developmental delays. Tester completes a questionnaire through interview with parent or caregiver. Any age. No parallel forms. Outcome measures: raw scores converted to scaled scores, then a summary value for a number of domains.

Table 11 Neuropsychological Assessments Timeline

Instrument	Information Source	Screening (Visit 1)	Baseline^ (Visit 2)	3-month [#] (Visit 5)	6-month [#] (Visit 8)
Primary Efficacy Outcome Neurocognitive Composite	Testing		Х	Х	Х
Stanford-Binet Fifth Edition (SB-5) / Mullen Scales of Early Learning (MSEL)	Testing	Х			х
Columbia-Suicide Severity Rating Scale	Interview	Χ		X	X
Stanford-Binet Working Memory Subscale Only	Testing		Х	X	
Conners' Continuous Performance Test (CPT-3/K-CPT-2)	Testing	X	х	x	x
Wechsler Processing Speed Index (PSI)	Testing		X	X	X
Wide Range Assessment of Memory and	Testing		Х	X	X

Learning-2 (WRAML-2)					
Peabody Picture Vocabulary Test – Fourth	Testing		X	X	x
Edition (PPVT-4)			^	^	^
Expressive Vocabulary Test – Second	Testing		X	X	x
Edition (EVT-2)					
Purdue Pegboard (PP)	Testing	Χ	X	X	X
Autism Diagnostic Observation Schedule (ADOS-2)	Observational		Х		X
Social Responsiveness Scale – Second	Parent/Caregiv				
Edition (SRS-2)	er/Informant or		X	X	X
	Self- Report				
Repetitive Behavior Scale – Revised (RBS-	Parent/Caregiv				
R)	er/Informant or		X	X	X
	Self Report				
Developmental Coordination Disorder	Parent/Caregiv				
Questionnaire (DCDQ)	er/Informant or		X	X	X
	Self Report				
Behavior Rating Inventory of Executive	Parent/Caregiv				
Function (BRIEF)	er/Informant or		X	X	X
	Self Report				
Adult/Child Behavior Checklist (CBCL	Parent/Caregiv				
ARF/CBCL)	er/Informant or		X	X	X
	Self Report				
Short Sensory Profile (SSP)	Parent/Caregiv				
	er/Informant or		X	X	X
	Self Report				
Vineland Adaptive Behavior Scales (VABS-	D 110				

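### The Time x Group slope test, carried over to every secondary outcome, does not suit CGI-Improvement, and the plan does not say which p-value enters the false discovery rate list

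*Combined protocol and SAP*

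**What the plan says.** Section 17 (objective 2) analyses the neurocognitive composite with a mixed-effects growth model over baseline, Month 3 and Month 6. The deciding result is named: "A significant interaction between Time and Randomization Group, with the everolimus group showing a more favorable outcome trajectory, will support the primary efficacy hypothesis". The individual slope is the key "dependent variable predicted by randomization group".

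The same section adds three further analyses:
- Conversion to a group difference at each visit: "Of particular interest is the group difference at end of treatment (6-month assessment").
- A repeat of the mixed model with each outcome's baseline score "treated as a baseline covariate to control for (instead of as a part of) the repeated measures".
- An endpoint ANCOVA, worded for the composite only.

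It then extends all this: "The same analysis strategy will be employed for secondary efficacy outcomes", with a false discovery rate correction. Section 17.1 applies a Benjamini-Hochberg correction across all secondary outcomes and lets only those that pass go forward as Phase III candidates.

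Table 12 lists CGI-S, CGI-I, the ADOS calibrated severity score and the SB-5 IQ scores as secondary efficacy outcomes. Their double-blind schedules (Tables 11 and 13A, with footnotes) are:
- CGI: severity only at baseline; Months 1, 3 and 6; optional at Months 2, 4 and 5.
- ADOS-2: baseline and Month 6.
- Full SB-5: screening and Month 6. The working memory subscale is also given alone at baseline and Month 3, so it has at least three points and is not affected.

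**The concern.** The lead test presumes an outcome measured before treatment and twice afterwards. CGI-I is not of that kind. It is a rating of improvement, so a treatment benefit shows as a difference in level from the first post-baseline visit, while the slope sees only what changes after that visit. A stable benefit gives a slope difference of zero.

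The consequence runs through the false discovery rate step. Section 17 tests main effects, interactions and cross-sectional differences, and nothing says which one represents each secondary outcome in the list. If the interaction is used for CGI-I, as the composite's deciding test suggests, a genuine effect may not be carried forward. If the choice is left open, the same data could pass or fail according to which p-value is entered.

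**Working it through.** **Inputs.** From Section 17.1: 20 per arm, one-sided 0.05, repeated-measures correlation r of at least .30. From Table 13A: CGI-I at Months 1, 3 and 6. Assumed, because the documents give no CGI-I effect or time course: a 0.80 SD difference at Month 6 (the size used in the plan's endpoint calculation), the shapes below, r = .3, .5 and .7, equal variances and correlations across visits, complete data.

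**1. The plan's own figures.** Endpoint comparison: SE = sqrt(2/20) = 0.316 SD; power = Φ(0.80/0.316 − 1.645) = 0.81 (noncentral t: 0.80), against 80% stated. At 0.65 SD: 0.66 (t: 0.65), against .65 stated. Repeated measures at 0.50 SD: f = 0.25, λ = f² × N × m/(1 − r) = 0.0625 × 40 × 3/0.70 = 10.71 on 2 and 76 df, power 0.827, against .83 stated. All three reproduce.

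**2. CGI-I slope over Months 1, 3 and 6.** The mean month is 3.33, the deviations are −2.33, −0.33 and 2.67, and their sum of squares S is 12.67. With δ the group difference at each visit, the slope difference is b = Σ(t − t̄)δ/S. Its SE is sqrt[((1 − r)/S) × 2/20] = 0.0743, 0.0628 and 0.0487 at r = .3, .5 and .7. Power = Φ(b/SE − 1.645).

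| Assumed shape | δ at Months 1, 3, 6 (SD) | b per month | Power, r = .3 / .5 / .7 |
|---|---|---|---|
| Stable from Month 1 | 0.80, 0.80, 0.80 | 0 | 0.05 / 0.05 / 0.05 |
| Complete by Month 3 | 0.27, 0.80, 0.80 | 0.098 | 0.37 / 0.47 / 0.65 |
| Linear from zero | 0.13, 0.40, 0.80 | 0.133 | 0.56 / 0.68 / 0.86 |
| Early, then fading | 1.00, 0.90, 0.80 | −0.039 | 0.015 / 0.012 / 0.007 |

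The Month 6 comparison has power 0.81 in every row. Using the t distribution lowers the figures slightly (for example 36-63% in the second row).

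**3. The other planned analyses, for CGI-I.** The baseline-covariate model and the ANCOVA both need a baseline score on the outcome, and CGI-I has none. The Month 6 group difference can be used.

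**4. ADOS-2 and full SB-5.** With two points, Time x Group is the between-arm difference in change. In one simulated data set (20 per arm, r = .5), the random-intercept model and the t-test on change gave the same estimate (0.265) and the same t (0.998). A random intercept, random slope, their covariance and a residual make four variance parameters, against three observable moments (two variances and one covariance), so that version needs a constraint. When fitted, it gave the same treatment estimate, 0.265.

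Efficiency: the variance of the change comparison is 2(1 − r) × 2/20 and that of ANCOVA is (1 − r²) × 2/20. The ratio is 2/(1 + r): 1.33 at r = .5 and 1.18 at r = .7. The plan's .83 also assumes three points; its formula with m = 2 gives λ = 7.14 and power 0.74.

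**The case against.** The strongest reply is that the plan carries over a strategy, not one test. Section 17 already contains a Month 6 difference, singles it out as of interest, and tests main effects as well. The 5% against 80% contrast is thus between two planned analyses. A reader might infer that a real global improvement present from Month 1 would be missed; the documents do not support that. The Month 6 comparison would have about 80% power to show it. CGI-S, also a secondary outcome, has a baseline: if its Month 6 effect were also 0.80 SD, a slope over 0, 3 and 6 months would have power of 0.69 to 0.95 at r = .3 to .7.

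The effect shapes are also assumptions. Under linear growth, the shape a growth model presumes, the slope does better than the Month 6 comparison at r = .7 (0.86 against 0.81).

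A reader might further infer that the test cannot be fitted, or asks the wrong question, for ADOS-2 and full SB-5. It can be fitted, and it compares change between arms, which is a valid question. Only the version with individual random slopes is unidentified, and Section 17 does not spell out the covariance structure.

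Finally, Sections 17 and 17.1 call the analyses predominantly descriptive.

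All of this stands. It does not settle which result speaks for CGI-I, and a descriptive aim does not remove the formal selection rule in Section 17.1.

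**Conclusion.** The point holds for CGI-I. The lead test is poorly matched to an outcome that has no baseline and already expresses change, two of the planned alternatives lack the baseline score they need, and nothing names the p-value that enters the false discovery rate list. The loss depends on the time course: almost all power if the benefit is stable from Month 1, roughly 15 to 45 percentage points if it is complete by Month 3, and between a loss of about 25 points and a gain of about 5 if it grows linearly. These figures rest on the assumed 0.80 SD, the assumed shapes, equal correlations and complete data. The schedule mismatch rests on the documents alone.

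For ADOS-2 and full SB-5 scores the issue is smaller: a valid test that is less efficient than ANCOVA, a growth model that needs a stated constraint, and a three-point power figure that does not carry over. This should be corrected before unblinded data are analysed; it does not undermine the trial.

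**What to change.** Add a short table to Section 17 giving, for each secondary outcome, the model and the single p-value that enters the false discovery rate list:
- **CGI-I:** the Month 6 group difference from a repeated-measures model with visit as a category and baseline CGI-S as covariate.
- **ADOS-2 and full SB-5 scores:** ANCOVA of the Month 6 score on the pre-treatment score (baseline for ADOS-2, screening for SB-5). If a mixed model is also reported, state that it has a random intercept only.
- **Outcomes with baseline, Month 3 and Month 6:** keep the growth model, and say whether the interaction or the Month 6 difference is the listed result.

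The cost is a few lines of text. Every value needed is already scheduled, and the models are no more complex than those planned. ANCOVA leaves out patients without a Month 6 value, but for a two-point outcome such patients contribute only a pre-treatment score, so little information is lost.
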